#### **Consent**

Prior to enrollment, all participants will view a video of the PI, [name] (in English), or another healthcare professional (in Spanish), explaining the study, what is involved, and its risks. Written text of this consent message appears below this video. After watching the video and reviewing the consent text, mothers who want to participate may select the “I Agree” button, and will be randomized into the study. Those who do not wish to participate may select the “I Do Not Agree” button and return the tablet to the hearing screening technician. We request that a traditional written informed consent be waived, as collecting patient signatures would require us to collect identifying information in an otherwise de-identified study.

No identifying information is collected in this study. All information collected is de-identified, and will be stored under a coded numerical variable name that is not linked to any identifying information.

Hearing screening techs, research assistants, and nurses who implement the study are trained to address patient questions as outlined in the Quick Guide. Patients with questions not immediately resolved per the Quick Guide guidelines will be referred to the TMW study team.

### **Confidentiality**

The raw data will only be made available to the PI and study personnel listed on the protocol. Survey participants’ will be stored under numerical codes and will not contain any identifying information. The data will be carefully monitored to protect patient privacy.

### **Recruitment**

The hearing screening tech, research assistant, or nurse will offer participation to all eligible subjects on the maternity ward. All mothers on the maternity ward or present in the NICU at Sacred Heart Hospital, University of Chicago Medical Center, or Baptist Hospital-Pensacola during the study protocol will be eligible to participate.

There will be no use of advertisements or additional materials for recruitment purposes. The hearing screening tech or research assistant will offer study participation to mothers in their rooms at the start of the newborn’s hearing screening. The Welcome and Consent Video in the TMW Tech Platform will describe the study in detail.

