### **Protocol**

We propose to perform a randomized implementation trial to evaluate the efficacy of various implementation methods of the TMW-Newborn educational intervention. The study will be

conducted in temporal proximity to the administration of the universal newborn hearing screen.

After routine delivery, postpartum mothers are admitted to the mother-baby unit for 48-72 hours. At Sacred Heart Hospital, study participation will be offered to every postpartum mother prior to discharge by a hearing screening technician, registered nurse, or registered hospital volunteer during the patient's hospital stay. Study participation will be offered to every mother whose child is receiving the hearing screening at the University of Chicago Medicine and Baptist Hospital-Pensacola. At the University of Chicago Medicine, study participation will be offered by a research assistant or hearing screening technician. At the Baptist Hospital-Pensacola, study participation will be offered by a nurse. The technician, nurse, or registered volunteer will give each mother an electronic tablet with the HIPAA Compliant TMW-Newborn Tech Platform that houses the TMW-Newborn intervention.

The patient experience through the TMW-Newborn intervention within the TMW Tech Platform is as follows:

- Participant selects language (English or Spanish) for viewing videos and completing surveys;
- Participant views Welcome and Consent Video, in which [name] (in English) or another health professional (in Spanish) introduce the study, explain participation, outline risks;
- Participants who agree to participate will then be randomized into one of four conditions:
  - Long TMW-Newborn intervention video without questions interspersed,
  - Long TMW-Newborn intervention video with questions interspersed,
  - Short TMW-Newborn intervention video without questions interspersed, or
  - Short TMW-Newborn intervention video with questions interspersed.
- Participant completes pre-intervention surveys: Baby SPEAK and non-identifying demographics items. These surveys take approximately 10 minutes to complete.
- Participant views TMW-Newborn intervention video, according to her randomized assignment outlined above.
- Participant completes post-intervention surveys: Baby SPEAK, UNHS, and fidelity of implementation.

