#### *Randomization*

The hearing screener, nurse, or volunteer will drop off tablets with participants, and only after the participants agree to participate by completing the tablet based consent will they be assigned to one of the four treatment conditions. The TMW-Newborn Web Platform will house the randomization tool that will randomize each participant into one of four treatment groups:

1. Long TMW-Newborn intervention video without questions interspersed,
2. Long TMW-Newborn intervention video with questions interspersed,
3. Short TMW-Newborn intervention video without questions interspersed, or
4. Short TMW-Newborn intervention video with questions interspersed.

There is equal likelihood of each randomization condition occurring.

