#### **Exclusion criteria**

Individuals that do not have a live birth at Sacred Heart Hospital, University of Chicago Medical Center, or Baptist Hospital-Pensacola or do not receive the UNHS at one of these locations will not be eligible for this study.

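### Does the broad recruitment wording admit mothers whom the exclusion criteria rule out?

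*Combined protocol and SAP*

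**What the plan says.** Four sections of the combined protocol bear on who enters the trial.

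- **Exclusion criteria.** Two categorical exclusions. The first begins "Individuals that do not have a live birth at Sacred Heart Hospital" and goes on to name the other two hospitals. The second covers those who "do not receive the UNHS at one of these locations will not be eligible for this study".
- **Recruitment.** Staff offer participation to eligible subjects on the maternity ward. The next sentence gives the pool as "All mothers on the maternity ward or present in the NICU at Sacred Heart Hospital" or at the other two sites. A later sentence has the technician or research assistant make the offer in the mother's room when the baby's hearing screen begins.
- **Protocol.** At Sacred Heart, "study participation will be offered to every postpartum mother prior to discharge", and the offer is made "by a hearing screening technician, registered nurse, or registered hospital volunteer". For the University of Chicago and Baptist Hospital the text reads "Study participation will be offered to every mother whose child is receiving the hearing screening".
- **Randomization** and **Consent.** Assignment is made by the tablet: "only after the participants agree to participate by completing the tablet based consent will they be assigned". No step that confirms live birth, place of birth or screening is described.

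**The concern.** Read word for word, the Recruitment sentence and the Sacred Heart sentence are wider than the Exclusion criteria. They would take in a mother on the ward after a stillbirth, a mother whose baby is not screened at the site and, under Recruitment, a mother in the NICU whose baby was born elsewhere. With tablet consent as the only gate described, such a mother could be approached and randomised. The data carry no identifiers, so her record might not be recognisable later.

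Three things would be at stake: an unwelcome approach to a bereaved mother, a study population defined differently at Sacred Heart than at the other two sites, and some dilution of the results by mothers who should not be in them.

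**Working it through.** **Plan's own figure.** The Participants section gives 10,000 mothers, with 2,500 in each of four equally likely conditions: 10,000 / 4 = 2,500. This agrees.

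**The sections side by side, for each group of mothers.**

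1. *Live birth and screen at the site, baby on the ward or in the NICU.* Eligible under every section. This is nearly everyone. A NICU mother of this kind raises no conflict. Recruitment mentions only the ward and mothers' rooms when it describes the offer, which leaves the place of approach unclear but not her eligibility.
2. *No live birth.* Excluded by the Exclusion criteria. Recruitment limits the offer to eligible subjects and times it, for technicians and research assistants, at the start of the baby's screen. The Chicago and Baptist offers depend on a child being screened. The Sacred Heart sentence has no such condition, but it follows directly on a description of admission after routine delivery, within a study set close in time to the hearing screen.
3. *Live birth at the site, baby not screened there.* Excluded. The link to screening removes her at two sites. At Sacred Heart she could be approached if the wording is taken literally.
4. *Baby born elsewhere but screened at the site.* Excluded on place of birth. The link to screening does not remove her, so here the inconsistency has real content. She is still a new mother for whom the video's message is apt.

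**Size, for group 3.** The only coverage rates in the documents are those for 2011 in the Background section on newborn hearing screening. Applying them to the sites is an assumption.

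- Not screened, national: 100 − 97.9 = 2.1%.
- Not screened, Illinois: 100 − 99.4 = 0.6%.
- Of 10,000 mothers: 0.006 × 10,000 = 60, and 0.021 × 10,000 = 210.
- Per arm of 2,500: 0.006 × 2,500 = 15, and 0.021 × 2,500 = 52.5.

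These counts suppose that all three sites enrol unscreened mothers at the full rate, although two sites tie the offer to screening. They are therefore high for group 3. Groups 2 and 4 cannot be counted, because the documents give no rate for either.

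**Effect on the results.** Let a fraction *p* of those enrolled be ineligible, and suppose pessimistically that the video has no effect on them. A true effect δ, whether a difference between arms or a change from before to after, is then estimated as

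(1 − *p*) × δ + *p* × 0 = (1 − *p*) × δ.

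With *p* = 0.006 this is 0.994 δ; with *p* = 0.021 it is 0.979 δ. Each further percentage point for the uncounted groups would take off another 1% of δ.

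**Bias between arms.** The arm is drawn by the tablet for each mother after consent. Whether she had a live birth, and where, is settled before that draw. The plan describes no removal of mothers after randomisation, so ineligible mothers fall equally among the four arms on average.

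**The case for a change.** The strongest case for a change concerns conduct rather than estimation. The Recruitment section's reference to eligible subjects is followed at once by a sentence saying who is eligible, and that sentence says all mothers. Its timing at the start of the screen is given only for technicians and research assistants, whereas Sacred Heart also uses nurses and volunteers at any time before discharge. The Consent section says "Hearing screening techs, research assistants, and nurses who implement the study are trained to address patient questions" and does not name volunteers. A literal reader could therefore hand a bereaved mother a tablet about talking to her newborn, and a line of text plus a brief check would prevent it.

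Some of this stands. The sections do not match, the protocol does not say which one governs, and no check is written down. The rest is weaker. An exclusion list normally overrides a general description of the pool. Approaching a bereaved mother would require staff to disregard a stated exclusion, the setting of routine delivery and the purpose of a visit built around a baby's hearing screen. An offer before discharge and an offer at the screen are compatible, since screening is part of the postpartum stay. The sentence on training concerns answering patients' questions, not judging eligibility. Whether ineligible records could be found later is unknown rather than ruled out: mothers complete demographic items and a UNHS survey, and the items are not reproduced in the document.

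**Conclusion.** The mismatch in wording is real but editorial, and it calls for no change to the plan. With the stated exclusions applied to the recruitment pool, the population is adequately defined and the conclusions are sound. If unscreened mothers entered at 0.6% to 2.1%, effects would be diluted to between 99.4% and 97.9% of their size, with no bias between arms. That rests on two assumptions: that the 2011 coverage rates describe the sites, and that the video has no effect on these mothers. Mothers without a live birth, or whose baby was born elsewhere, are not counted for want of any rate. The concern for bereaved mothers is legitimate, but it depends on a strained reading that ward staff would be expected to resolve sensibly. If the protocol is revised for other reasons, the three sections could be aligned at the same time, with a word on NICU mothers and on whether a scheduled screen suffices. No result depends on it.
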